13.1 Primary Efficacy Endpoint

The primary efficacy variable is the FSIQ score measured by the WPPSI-III or WISC-IV tests. The primary efficacy endpoint is the change in the FSIQ score over a 2 year period. A random coefficient model is used to calculate the slope (per year) of FSIQ over the entire study period and for each subject. Factors in the model will include visit and testing sequence, with change in FSIQ score as the dependent variable. Random terms include both intercept and visit. The model will use an unconstructed covariance matrix unless another covariance structure provides a better model fit. Subjects with less than one year of treatment duration are excluded from the analysis. Once the slope and 95% confidence interval are derived, the slope and lower limit of the confidence interval are multiplied by 2 to determine the average change in FSIQ and its lower limit over a 2-year window. The treatment will be considered successful if the lower 95% confidence limit of the mean change excludes a decline of greater than 5 points over a 2-year window.

All available data will be included in the analysis and the analysis will be stratified by testing sequence.

- Sequence 1: WPPSI-III (first or second form) at all time points
- Sequence 2: WPPSI-III (first or second form) at Baseline and (WPPSI-III or) WISC-IV at all post-baseline time points
- Sequence 3: WISC-IV at all time points

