3.4 Sample Size Determination

The sample size calculation assumes each child will have 2 post-treatment test results from the WPPSI-III and /or WISC-IV tests at least 2 years apart. The goal is to exclude a mean 2.5-point loss per year in IQ score. Given a 2-side Type I error rate of 0.05, if the mean IQ score at baseline is 100, the standard deviation is no larger than 16, and the correlation between the 2 test results is 0.8, a sample size of 45 subjects will yield at least 90% power.

To account for the possibility of dropouts and to have reasonable precision for estimating change in IQ from the time a child reaches at least age 30 months until the end of the study, approximately 60-80 Kuvan-responsive subjects will be enrolled in the study.

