4.1 Analysis Populations

The Full Analysis set (FAS) will consist of all subjects who enroll into the study.

The Enrolled population will consist of all subjects who enter Part 2 of the study and met the inclusion/exclusion criteria per CRF. This population involves subjects who respond to Kuvan and had a Bayley-III or IQ test score ≥ 80 within 6 weeks of determination of Kuvan responsiveness in Part 1. Kuvan responders consist of all subjects with at least 30% average reduction in blood Phe concentration calculated as the mean of the weekly percent change from baseline at Week 1, 2, 3 and 4 in Part 1.

The Efficacy population will consist of all subjects from the Enrolled population who have at least two WPSI/WISC assessments.

The Safety population will consist of all subjects who have received any study drug in the FAS population.

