13.3.1 IQ Scores

An exploratory analysis to assess the effect of blood Phe control with Kuvan on IQ over a 7 year observation period will examine the stability from baseline in the FSIQ score. Baseline for FSIQ score is defined as the first assessment in FSIQ score after determination of Kuvan responder status. The analysis will be performed using a repeated measures model with factors visit and testing sequence, with change in FSIQ score as the dependent variable. The model will apply an unconstructed covariance matrix unless another covariance structure provides a better model fit. 95% Confidence intervals will be reported annually with emphasis at Year 7. A figure of LS-means and the 95% CI will also be displayed.

Specific subsets are summarized to further examine the robustness of the above Year 7 results. The following subsets will be used:

- Subjects enrolled in study due to an exemption are excluded
- Subjects with a Baseline FSIQ score at the recommended visit (Month 2)
- Subjects assigned to Sequence 2 with Baseline as the first assessment in FSIQ score after determination of Kuvan responder status
- Subjects assigned to Sequence 2 with Baseline as the first assessment in FSIQ score at the recommended visit (Month 2)

All subset summaries include a repeated measure analysis similar to the original analysis. Sequence is removed from the analyses where the subset is based on sequence.

Furthermore, the mean change from baseline in FSIQ score at Year 7 will be summarized descriptively by sequence and overall. A paired t-test will be performed across all subjects with a 95% CI and p-value reported at Year 7. An additional subset examining subjects without a Baseline FSIQ score at the recommended visit (Month 2) is presented as well.

In addition, descriptive statistics of each observed composite and subtest IQ score and its respective change in IQ score from Baseline will also be presented by sequence and overall and listed at each time point. The change from Baseline of each composite score will be plotted as well.

Proportion of subjects with a specified change from Baseline in each composite and subtest IQ will also be summarized at each time point. The specific change is as follows:

	SAP PKU-015, Version 3.0	Page 24 of 31
---	--------------------------	---------------

- FSIQ: absolute change greater than 7
- Verbal IQ: absolute change greater than 10
- Performance IQ: absolute change greater than 10

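### SAP 13.1 models change in FSIQ with a free intercept and no rule for the zero first row, so the primary slope either skips the first interval or carries too large a standard error

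*SAP*

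**What the plan says.** SAP 13.1 sets the target: "A random coefficient model is used to calculate the slope (per year) of FSIQ over the entire study period and for each subject". It then specifies the model: "Factors in the model will include visit and testing sequence, with change in FSIQ score as the dependent variable", and "Random terms include both intercept and visit". The slope and its lower 95% limit are doubled, and the treatment succeeds if the doubled limit excludes a loss of more than 5 points.

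Section 13.1 does not name the assessment from which change is measured, does not fix the intercept at zero, and does not say whether the first assessment enters as a row with change zero. Two other statements bear on this without settling it:

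- Section 13.1 adds: "All available data will be included in the analysis". This leans towards keeping the row but does not say that a derived zero counts as data.
- Section 13.3.1 gives a reference point, "Baseline for FSIQ score is defined as the first assessment in FSIQ score after determination of Kuvan responder status", but for the exploratory repeated-measures model, and it is also silent on the zero row.

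Section 4.1 admits to the Efficacy population children "who have at least two WPSI/WISC assessments". Section 3.4 "assumes each child will have 2 post-treatment test results".

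**The concern.** The doubled slope and its lower limit decide whether the trial succeeds. Two programmers following 13.1 faithfully can fit different data sets.

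- **Reading A, first row left out.** The free intercept takes up all movement between the first and second test, and the success rule ignores the intercept. An early loss therefore drops out of the criterion. A child with exactly two tests supplies one row and no slope from that child's own data.
- **Reading B, zero row kept.** The first row is zero by construction and has no variance, but the model assigns it intercept and residual variance like any other row. The reported standard error is then too large.

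Neither reading is as good as modelling the observed score, which is what a slope of FSIQ calls for.

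**Working it through.** **Inputs from the SAP.** SD 16, correlation 0.8 and 45 subjects (3.4); two-sided 5% level ("Given a 2-side Type I error rate of 0.05"); margin 2.5 points a year, or 5 over 2 years (3.4, 13.1); test schedule (Table 3.2.1); 7 years of treatment (3.2).

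**Assumptions not in the SAP.** Between-child slope SD 0 to 2 points a year; dropout 0 to 10% a year; entry age uniform over 0 to 7 years; 65 children for the exact calculation and 45 for the simulation.

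**1. The SAP's own figure.** SD of a paired change = 16 × √(2 × 0.2) = 10.12. SE = 10.12/√45 = 1.51. Power = Φ(5/1.508 − 1.96) = 91% (90.0% with the noncentral t). The stated figure of at least 90% is reproduced, and it uses both scores. If every child had two tests exactly 2 years apart, reading A would leave one row per child, all at the same time. Intercept and time would be collinear and no slope could be estimated.

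**2. Reading A, balanced annual tests at years 0 to 7.** The sum of squares of time is 42 with year 0 and 28 without it. Residual variance = 256 × 0.2 = 51.2. Slope variance per child is 51.2/SS plus the squared slope SD:

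- Slope SD 0: 1 − 28/42 = 33% of the information lost.
- Slope SD 0.7: (1.219 + 0.49)/(1.829 + 0.49) = 0.74, so 26% lost.
- Slope SD 2: (1.219 + 4)/(1.829 + 4) = 0.895, so 11% lost.

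**3. Reading A, Table 3.2.1 schedule.** Exact generalised least squares with the sequence term, 65 children, dropout 5% a year; SE of the 2-year change:

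| Slope SD | 0 | 0.3 | 0.7 | 1.5 | 2.0 |
|---|---|---|---|---|---|
| Observed FSIQ | 0.455 | 0.462 | 0.492 | 0.605 | 0.698 |
| Reading A | 0.595 | 0.601 | 0.626 | 0.724 | 0.807 |
| Information lost | 42% | 41% | 38% | 30% | 25% |

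Over dropout of 0 to 10%, the loss runs from 42% down to 23%, and the SE excess from 31% down to 14%.

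**4. Simulation of all three fits.** REML, 45 children, staggered entry, dropout 6% a year, 300 replicates, on average 4.85 tests per child, 7% of children with exactly two. SE of the annual slope:

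| Slope SD | 0 | 1 | 2 |
|---|---|---|---|
| Observed FSIQ: model SE / true SD | 0.289 / 0.296 | 0.322 / 0.329 | 0.423 / 0.418 |
| Reading A: model SE | 0.378 | 0.408 | 0.494 |
| Reading A: excess over observed FSIQ | 31% | 27% | 17% |
| Reading B: model SE / true SD | 0.328 / 0.298 | 0.360 / 0.330 | 0.447 / 0.420 |
| Reading B: overstatement | 10% | 9% | 7% |

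Monte Carlo error on SE ratios is about 4%. With a balanced 8-visit schedule, reading B's overstatement was 12% at slope SD 0 and 5% at 0.5, and none was visible at 1 or 2. A further simulation on the Table 3.2.1 schedule put reading A's SE excess at about 23% to 28% and reading B's overstatement at about 7% to 14%.

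**5. Chance of success (same simulation).**

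| True slope | Reading A | Reading B | Observed FSIQ |
|---|---|---|---|
| −1.5 a year, slope SD 0 | 72% | 88% | 93% |
| −1.5 a year, slope SD 1 | 71% | 84% | 90% |
| −2.5 a year (at the margin), slope SD 0 to 2 | 2.0–4.3% | 2.0–3.7% | 3.3–5.0% |

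At a true slope of 0, every fit succeeded in every replicate. Monte Carlo error on success rates is about 2 to 3 points, so the last row shows no inflation from change-score coding. The higher figures for observed FSIQ go with a model SE that matches its true SD.

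**6. Early loss of 5 points, then flat.** With 65 children, observed FSIQ gives a 2-year change of about −1.5 (lower limit about −2.4). Reading A gives 0.0 (lower limit −1.96 × 0.626 = −1.2). The simulations agree: 2 × −0.73 = −1.46 in one and about −1.2 in the other, against about 0.0 under reading A. All of these meet the criterion. Each point of early loss moves the observed-score 2-year change by −0.27 to −0.34. At slope SD 0.7 the room to the margin is 5 − 1.96 × 0.492 = 4.04 points, so a loss of 4.04/0.34 = 12 to 4.04/0.27 = 15 points would be needed. Over all assumptions the figure is about 14 (10.5 to 15).

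**The case against.** Change is FSIQ minus a constant for each child, so over the same rows each child's slope is identical, and 13.1 itself defines the endpoint as a change. On this view only a row rule is missing, and one clause would supply it. The wording favours reading B, which is conservative, and its SE excess is not visible in a balanced design once slopes vary by 1 point a year or more. Section 13.1 also allows a better-fitting covariance structure. Section 3.4 says at least 2 years apart, so the collinear case is artificial, and a mixed model still predicts a shrunken slope for a child with two tests. An early loss would show in the 13.3.1 analyses. Section 3.6 records that data were examined in 2012, and section 15 that the 13.1 analyses are new in Version 3.0, so a further change to the primary model is not trivial.

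Much of this stands. Reading B is the more likely one, the two-test design is only an illustration, and the larger figures belong to reading A. But a row rule alone would fix one of two inferior analyses: it would settle either the missing first interval or the misfitted zero row. A covariance structure that gave the first row its own variance could repair reading B, but 13.1 does not specify it, and the choice would depend on the data. The exploratory analyses do not enter the success rule.

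**Conclusion.** The concern holds and should be fixed. As written, 13.1 does not fix the data set for the primary model, and both readings are inferior to modelling observed FSIQ. Reading A does not deliver a slope over all of follow-up and raises the SE by about 14% to 31%. Reading B leaves the estimate almost unchanged and overstates the SE by about 7% to 10% on a staggered schedule, less or not at all on a balanced one with varying slopes.

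The limits are clear. With a linear trend neither reading is biased, no inflation of false success from the change-score coding was found, and no reversed verdict is claimed. The choice matters mainly for true slopes between about −1 and −2.5 points a year. The percentages depend on assumed slope SD, dropout, entry ages and number of children. The gap in the text does not.

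**What to change.** In 13.1, make observed FSIQ at every assessment, including the first, the dependent variable. Use actual years since the first FSIQ as a continuous fixed slope, with a random intercept and a random slope on that time. Keep the testing-sequence term, the doubling and the 5-point criterion. Continuous time suits a slope per year: Table 4.5.1 lets Month 12, counted from the first assessment, run from Day 2 to Day 548. Report the change-score model as a sensitivity analysis, stating its reference assessment and whether the zero row is included.

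The cost is one sentence of SAP text and a changed model statement; no new data are needed. Because this is a late change to the primary model of an open-label study, the change and its reason must be documented and both results shown.

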13.1.1 Supportive Analysis of the Primary Endpoint

A supportive analysis to the primary endpoint will be the mean difference between the last two available FSIQ assessments that were two years apart. This analysis was conducted to provide additional data on the 2-year analysis window when the subject was oldest, as the reliability of IQ testing in children increases over time. A 95% confidence interval will be calculated using a paired t-test. The result of a lower 95% confidence limit of the mean

	SAP PKU-015, Version 3.0	Page 22 of 31
---	--------------------------	---------------

difference excluding a decline of greater than 5 points is deemed favorable and supports a positive primary analysis result.

13.2 Secondary Endpoints

The secondary efficacy variables are:

- Growth measurements (height, weight, head circumference z-scores)
- Neurocognitive testing results (Bayley-III) in children age 0 to less than 30 months old.

A subject listing of Bayley-III results and growth parameters (height, weight, and head circumference assessments and corresponding percentile and z-score) will be provided..

13.2.1 Growth Measurements

The change in height, weight, and head circumference from baseline will be assessed at each scheduled visit. In addition, height, weight, and head circumference will be converted to z-score based on CDC Clinical Growth Charts (WHO Growth Charts for subjects less than 24 months) and the percentile, z-scores, and change in z-score from baseline of these growth variables will be summarized for each age group and all ages combined at each schedule time point. Growth charts using z-scores will be provided in each scheduled time point.

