3.3 Study Population

Individuals eligible to participate in this study must meet all of the following criteria:

- Parent(s) or guardian(s) willing and able to provide written, signed informed consent after the nature of the study has been explained, and prior to any research-related procedures.
- Parent(s) or guardian(s) willing and able to comply with all study procedures.
- Female subjects of childbearing potential (as determined by the investigator) and sexually mature male subjects willing to use a medically accepted method of contraception throughout the study. Female subjects of childbearing potential willing to undergo periodic pregnancy tests during the course of the study
- Established diagnosis of PKU with hyperphenylalaninemia (HPA) documented in the medical record by at least 2 blood Phe concentrations $\geq 360 \mu\text{mol/L}$ (6 mg/dL) taken at least 3 days apart
- Documented blood Phe control (defined by the standard used at each treatment center) prior to study enrollment, if applicable (eg, the subject is old enough for these data to be collected); blood Phe concentrations for subjects < 6 months old at Screening must be considered controlled and stable by the Investigator

	SAP PKU-015, Version 3.0	Page 9 of 31
---	--------------------------	--------------

- Willing to adhere to a prescribed Phe-restricted diet in order to maintain blood Phe concentrations within the recommended ranges established at the subject's study site
- Age 0 to 6 years, inclusive, at Screening

Individuals eligible to participate in Part 2: Neurocognitive Study must meet **all** of the following criteria:

- Completion of Week 4 visit in Part 1
- Responsive to Kuvan during Part 1, defined as a $\geq 30\%$ average reduction in blood Phe concentration calculated as the mean of the weekly percent change from baseline in blood Phe concentration at Weeks 1, 2, 3, and 4
- Bayley-III or IQ test score ≥ 80 when tested within 6 weeks of determination of Kuvan responsiveness in Kuvan-responsive subjects

Individuals who meet any of the following exclusion criteria will not be eligible to participate in the study:

- Has known hypersensitivity to Kuvan or its excipients
- Use of Kuvan or any investigational product or investigational medical device within 30 days prior to screening, or requirement for any investigational agent prior to completion of all scheduled study assessments

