4.2 Treatment Group Presentation

All subjects enrolled into the study will be administered 20 mg/kg Kuvan daily.

Efficacy and safety analysis results will be presented by age group at enrollment, and all ages combined except for the Neurocognitive summary. The following age groups will be used for all subjects enrolled in Part 2:

- 0 – 1 year old (0 to < 1)

	SAP PKU-015, Version 3.0	Page 12 of 31
---	--------------------------	---------------

- 1 - 2 years old (≥ 1 to < 2)
- 2 - 4 years old (≥ 2 to < 4)
- 4 – 6 years old (≥ 4 to < 7)

In addition, safety analysis may also be presented during Part 1 by the following group:

- Part 2 Enrolled
- Part 2 Not Enrolled
- Overall

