7 DEMOGRAPHICS AND BASELINE CHARACTERISTICS

Subject demographics (age, sex, ethnicity, and race) and baseline characteristics (weight, height, head circumference, blood Phe concentration, prescribed dietary Phe, and blood tryptophan and tyrosine concentration) will be summarized separately by age group at enrollment and all ages combined. A separate table will summarize the neurocognitive testing (Bayley-III, WPPSI-III and WISC-IV) at Month 2 in Part 2.

Age, sex, ethnicity, and race will be summarized using the number and percentage of subjects with a particular attribute. The denominators for percentages will be based on the number of subjects in each age group. Weight, height, head circumference, blood Phe concentration, blood tryptophan and tyrosine concentration, and neurocognitive tests will be summarized using descriptive statistics including n, mean, SD, median, min, max, 25th percentile, 75th percentile. In addition, the percentile and z-scores of weight, height, and head circumference based on CDC Clinical Growth Charts (WHO Growth Charts for subjects less than 2 years of age) will be summarized using descriptive statistics.

A subject listing of demographics and baseline characteristics will also be provided.

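### From Month 24, z-score change from baseline in the two youngest age groups is a CDC value minus a WHO value, and the SAP neither separates nor flags these changes

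*SAP*

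**What the plan says.** Section 13.2 lists "Growth measurements (height, weight, head circumference z-scores") among the secondary efficacy variables. Section 13.2.1 says the three measures are "converted to z-score based on CDC Clinical Growth Charts (WHO Growth Charts for subjects less than 24 months"). In the same sentence it plans that the "change in z-score from baseline of these growth variables will be summarized for each age group and all ages combined". Section 7 describes baseline z-scores with the same split, "based on CDC Clinical Growth Charts (WHO Growth Charts for subjects less than 2 years of age").

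Eligibility in section 3.3 is "Age 0 to 6 years, inclusive, at Screening". Two of the four reporting groups in section 4.2 lie wholly below the chart boundary at entry: "0 – 1 year old (0 to < 1") and "1 - 2 years old (≥ 1 to < 2"). Section 3.2 regards the study as complete when about 45 subjects have had 7 years of treatment.

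Section 13.3.4 uses change in weight and height z-score again, correlating it with change in prescribed dietary Phe. The SAP does not keep one reference per child, bridge the two charts or mark changes that span both.

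**The concern.** Using each chart at its own ages is a conventional way to describe a child's growth status at one time point. A change score is different. When baseline is scored on one reference population and follow-up on another, the difference contains the child's relative growth plus the gap between the two references at that age.

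Growth is a secondary objective (section 3.1), and the study has no control arm (section 3.5) in which the same gap would arise and cancel. In the all-ages summary, cross-chart changes from the youngest children are averaged with single-chart changes from the older ones. In the section 13.3.4 correlations the extra term is present for some children and absent for others according to entry age. If entry age is also related to dietary change, the correlation can be distorted.

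**Working it through.** The plan states no figure on this point, so there is none to reproduce. The check applies the chart rule to the visit schedule.

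**Inputs from the SAP.** The chart boundary is 24 months (sections 7 and 13.2.1). Entry is from age 0 (section 3.3). The age groups are those of section 4.2. The schedule for height and head circumference in section 4.5 is Week 4, Month 3, then six-monthly. Taken to Month 84, that is 2 + 14 = 16 post-baseline visits. Weight has more early visits but the same six-monthly schedule later.

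**Which age selects the chart.** The SAP does not say. Age at measurement is the natural reading. The document refers explicitly to age group at enrollment where it means entry age, and its parallel 30-month limit for Bayley-III concerns a test chosen by age at assessment (section 3.2).

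**Decomposition.** For a child with a WHO baseline who is measured at time t after 24 months of age:

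reported change = z_CDC(t) − z_WHO(0) = [z_WHO(t) − z_WHO(0)] + [z_CDC(t) − z_WHO(t)]

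The first bracket is change on a single reference. The second is the chart gap, d.

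**Visits affected.** A visit is cross-chart when entry age plus study month is at least 24. Week 4 is counted as month 1.

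| Age at entry (months) | First cross-chart visit | Cross-chart visits of 16 |
|---|---|---|
| 0 | Month 24 | 11 |
| 6 | Month 18 | 12 |
| 12 | Month 12 | 13 |
| 18 | Month 6 | 14 |
| 23 | Week 4 | 16 |

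A child enrolled at 6 months crosses the boundary at study month 18. That leaves 84 − 18 = 66 months, or 5.5 of 7 years, on the cross-chart side.

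**Share of each group affected**, assuming entry ages are uniform within the group:

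- 0 to <1: 0% at Month 12, 50% at Month 18, 100% from Month 24.
- 1 to <2: 50% at Month 6, 100% from Month 12.

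The 100% from Month 24 needs no uniformity assumption, only visits at their nominal times. The Month 24 window opens at Day 639 (639 × 12/365 = 21.0 months), so a child enrolled near birth and seen early could still be on the WHO chart at that one visit.

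**Effect on the mean.** With no true change, mean reported change = p × d, where p is the share of children with data at that visit who have crossed charts.

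- In the two youngest groups from Month 24, p = 1 and the shift is d. An assumed d of 0.1 to 0.5 z gives 0.1 to 0.5 z.
- In all ages combined, with p assumed at 20% to 60%, the shift runs from 0.2 × 0.1 = 0.02 z to 0.6 × 0.5 = 0.30 z.

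Neither d nor p is in the document. If both ends of each change use the same reference, d drops out at every visit.

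**The case against.** **The gap is not shown.** The SAP contains no chart values, so it establishes neither the size nor the sign of d, nor whether d is similar for height, weight and head circumference. This stands. The document shows that the two references are mixed in one difference; it does not show a bias of known size.

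**No planned inference is affected.** A reader might infer that the chart switch alone could make a growth change look statistically significant. The SAP does not support that. Section 13.2.1 plans summaries, the descriptive statistics listed in section 4 include no confidence interval, and growth has no test or success criterion. An illustration with 15 children and an SD of change of 0.7 (both assumed) also depends on the method. The 95% half-width is 1.96 × 0.7/√15 = 0.35 z by the normal approximation but 0.39 z with t. With 10 children and t it is 0.50 z, at the top of the assumed range.

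**The effect could be recognized.** A reader might also infer that a step at 24 months could not be told from a drug or diet effect. That goes too far. Raw changes, observed z-scores and percentiles are reported at each time point, individual values are listed, and the two older groups, which never switch charts, are shown separately. Equally, without a control arm no growth change could be attributed cleanly to drug even on one reference. What remains is that the summarized z-score change itself mixes two things, and the reader must notice this unaided.

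**Age at enrollment may be meant.** In that case no child would switch charts. The SAP does not say so, and its other wording points the other way.

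**Conclusion.** The point holds as a minor one. On the natural reading, section 13.2.1 defines a secondary efficacy summary that, for children enrolled under 24 months, becomes a CDC value minus a WHO value once they pass that age. At nominal visit times this covers every change from Month 24 in the two youngest groups. These values feed the all-ages summary and the section 13.3.4 correlations. This is a consequence of a stated rule rather than of omitted detail.

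Its numerical size is unknown. The ranges of 0.1 to 0.5 z for the youngest groups and 0.02 to 0.30 z for all ages rest wholly on assumed values. The document does not support a claim that a growth effect will be falsely reported, only that the summary cannot by itself separate growth from the change of reference.

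Unaffected are raw changes, observed z-scores, changes measured before 24 months of age, children enrolled at 24 months or older, and the primary FSIQ analysis.

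**What to change.** 1. State in sections 7 and 13.2.1 that age at measurement selects the chart for observed z-scores.
2. For children under 24 months at baseline, add change summaries within one reference: baseline to the last visit under 24 months on WHO, and from the first visit at or after 24 months onward on CDC.
3. Keep the cross-chart change from baseline, but only as a separate summary labelled as spanning two references.
4. Exclude cross-chart changes from the all-ages change summary and from the section 13.3.4 correlations, or repeat those analyses without them.

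No new data are needed. The cost is SAP wording and one extra derivation. The CDC segment starts from an on-treatment value, so it does not measure change from before treatment, and a child enrolled just under 24 months contributes almost nothing to the WHO segment. If cross-chart changes are excluded, the pooled long-term change summary has fewer children. Deleting the baseline-to-Year-7 change in the youngest groups altogether would cost more than labelling it and is not needed.
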